 Adults unable to consent (i.e., cognitively impaired adults) *	

6.2 For each of the above selected categories, describe the inclusion and exclusion criteria. Indicate age range, gender, and ethnicity.

Inclusion requires that children are aged 5.0-6.9 years at the time of enrollment with a parent-reported sleep onset of \geq 60 min after parents' desired bedtime at least three nights per week. Equal numbers of boys and girls will be enrolled. Children are *excluded* for the following reasons:

- All sleep disorders as indicated on the telephone screener or by clinical cut-off scores on the Children's Sleep Habits Questionnaire (CSHQ),^{49, 50} except for insomnia or DSWPD⁵¹ as features of these disorders are directly targeted by the intervention. Secondary analyses will explore if outcomes differ among participants with or without parent-reported symptoms consistent with these diagnoses.
- Physical abilities that interfere with assessments (e.g., visual impairment), developmental disabilities (e.g., autism, attention-deficit/hyperactivity disorder (ADHD), pervasive developmental disorder), epilepsy or other neurological disorders, metabolic disorders, medical conditions that commonly require treatments or assessments during the night (e.g., cancer, diabetes, active asthma), current infection or lead poisoning; a head injury involving loss of consciousness in the past 6 months.
- Current use of medications affecting daytime sleepiness, the circadian system, or light sensitivity.
- Eye disorders or color blindness (determined with Ishihara Color Vision Test); corrected vision with eyeglasses is permitted.

One adult parent of each participating child will also take part in the study. Parents must be able to provide consent and to complete the interview at the end of the study.

6.3 Describe the total number of subjects to be enrolled locally under this IRB approval. If obtaining specimens, specify the maximum number of specimens needed for this project.

We expect to enroll 60 children and 60 parents. We will aim to enroll 30 girls and 30 boys. Each child will provide a total of 24 saliva samples across the research protocol, for a total number of 1,440 samples expected to be collected as part of this project.

7.0 Recruitment Methods:

7.1 Select the methods used to recruit individuals.

 Email	 Screening of the Electronic Medical Record (EMR)

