Light Exposure (Aims 1 and 2). The actiwatch (ActLumus, Condor Instruments) is equipped with a high quality light sensor that assess light exposure in both photopic and melanopic lux. These data provide an objective measure of the child's light exposure throughout the protocol

(including compliance with the home lighting intervention) and will be used to examine changes in habitual light exposure.

Dim Light Melatonin Onset (DLMO) (Aim 2). At the end of the baseline and intervention periods, the child will come to the laboratory for a circadian assessment. The child will enter the dim-light (< 10 lux) laboratory suite 4.5 h before their habitual bedtime (average parent-reported bedtime across previous five days). Throughout the assessment, researchers will play with the child, providing toys and games specific to their interests. Starting 3.5 h before habitual bedtime, saliva samples will be collected in 30 min intervals, then 20 min intervals in the hour before habitual bedtime, continuing until 2 h past bedtime for a total of 12 saliva samples. Saliva samples will be obtained and stored using our standard published methods.⁶⁴ The child mouths/chews on one end of a braided cotton roll for 1-2 min. Children will remain in a sitting posture for 5 min before and during each saliva sample.⁶⁵ Lux levels will be obtained during each saliva sample using a research photometer (ILT2400; International Light Technologies, Inc.) held approximately 5 cm adjacent to the child's eye and directed in the angle of gaze. Samples will be immediately centrifuged and stored in a minus 80° C freezer. Following the completion of data collection, samples will be assayed by technicians blind to the study conditions. Saliva samples will be stored in the UA Biorepository and then sent to SolidPhase Inc. (Portland, ME) for assays. DLMO will be computed as the linear interpolated clock time at which melatonin levels cross (and remain above) 4 pg/mL.⁶⁶ The data will be used to examine changes in DLMO, a marker of circadian timing.

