Participants will be enrolled in the study for a total of 5 consecutive weeks in addition to the time taken for screening and enrollment itself. The estimated time for parents to complete the online questionnaires each time (twice) is 30 min. Each of the 3 initial training visits (including pupillometry and cognitive testing) are expected to last approximately 1h. The daily diaries (sleep diary, media diary) will take 10-15 min each day. Each of the 2 evening visits to the sleep lab (DLMO assessments) are expected to take approximately 7h. Children in the amber-tinted glasses intervention will be asked to wear them for 1h each night for 2 weeks. The qualitative interview is expected to last approximately 30 min.

10.4 If any biological specimens (blood, urine, tissue, etc.) are being collected for research, state the amount (ml/tsp/tbsp, etc.), method, frequency, and type of specimen to be collected and what the specimen will be used for.

Saliva will be collected during two one-evening visits to the University of Arizona Center for Sleep, Circadian & Neuroscience Research. Starting 3.5 h before habitual bedtime, saliva samples will be collected in 30 min intervals, then 20 min intervals in the hour before habitual bedtime, continuing until 2 h past bedtime for a total of 12 saliva samples per visit. The child mouths/chews on one end of a braided cotton roll for 1-2 min, which is then immediately placed in a tube and centrifuged, resulting in ~2 mL of saliva per sample. The specimen will be used for determining changes in the concentration of melatonin throughout the evening in order to calculate DLMO, a marker of circadian timing.

10.5 If the study is a clinical trial:

a) Confirm registration with <https://clinicaltrials.gov/> has been completed:

This study is not a clinical trial:

Registration complete:

Registration pending:

b) If the Principal Investigator (PI) does not possess a medical license, describe the scope and nature of the PI's previous clinical trial experience, including other studies they have led or participated in as Co-Investigator. If applicable, describe the previous clinical trial experience for the appointed Responsible Physician.

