Comfort of child participants during study activities: It is up to the parent to determine whether they would like to keep trying to encourage their child to complete the activity, but we will never force a child to continue with a study activity against their will. If the child is expressing clear discomfort with a study activity, the study team will pause the activity and give the child a break and discuss with the parent. At the parent's request we will try to engage the child in the study activity again. If they continue to express discomfort, then the study team will stop the study activity. During the in-lab salivary assessment, this may mean skipping the currently scheduled saliva sample and coming back to the child in 20-30 minutes to see if they are willing to try the next sample. Because we are keeping kids up past their bedtime for the two salary melatonin assessments, they can sometimes get overtired and cranky. We find that a little break and encouragement from the parent or a snack often allows the child to reset and finish the assessment.

Parental distress when completing questionnaires: This distress would be expected to be only transient, and parents will be reminded that they can skip any question they do not feel comfortable answering.

Maintaining participant confidentiality: Children will be assigned ID numbers upon enrollment in the study and these numbers will be used in all data records. Parent contact information, signed consent forms, and the code to match ID numbers to participants will be kept separately in a secure location in the locked laboratory. All data records will be maintained on password protected computers in the Sleep and Development Laboratory, only accessible to the appropriate study researchers.

Participants will be informed that they can withdraw from the study at any time and will receive pro-rated compensation.

13.0 Costs, Compensation, and Injury:

13.1 Describe any costs, monetary and non-monetary, that subjects may incur. This includes time.

There are no costs to subjects except for their time.

13.2 Discuss the amount of compensation (monetary and/or non-monetary) subjects may receive. Describe if compensation will be prorated.

For completing the study protocol, families are compensated a total of \$400. Children receive small non-monetary gifts for completing each circadian assessment. For any family who chooses to terminate study participation, compensation will be pro-rated as follows:

Baseline:

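### Does the DLMO saliva schedule contradict its own count of 12 samples per visit?

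*Protocol*

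**What the plan says.** Section 10.2 (5.B Measures, DLMO) sets the timetable in two pieces. The first is "Starting 3.5 h before habitual bedtime, saliva samples will be collected in 30 min intervals", and the second is "then 20 min intervals in the hour before habitual bedtime, continuing until 2 h past bedtime for a total of 12 saliva samples". Section 10.4 repeats the same schedule, ending "continuing until 2 h past bedtime for a total of 12 saliva samples per visit". Neither section gives a separate interval for the two hours after bedtime or lists individual sample times.

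Section 6.3 gives the specimen totals: "Each child will provide a total of 24 saliva samples across the research protocol, for a total number of 1,440 samples".

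The outcome is defined in section 10.2: "DLMO will be computed as the linear interpolated clock time at which melatonin levels cross (and remain above) 4 pg/mL".

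Section 12.2, on the comfort of the child, allows staff to skip a scheduled sample when a child is unhappy and describes "coming back to the child in 20-30 minutes to see if they are willing to try the next sample".

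**The concern.** A reader who lays the samples out on a time line gets nine by bedtime and then has two hours left to cover. If the word for carrying on is taken to extend one of the two stated intervals, the total exceeds 12 under either. On that reading the schedule and the count cannot both be right, and the specimen total in section 6.3 would be too low.

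Sample times matter because DLMO is one of the two outcomes named in the Aim 2 hypothesis. It is read by interpolating between neighbouring samples, and melatonin must then stay above the threshold. The spacing sets how wide the interpolation bracket is, and the last sample sets how late a crossing can be seen and confirmed. The children enrolled are those whose sleep onset is at least 60 min after the desired bedtime (section 6.2), so some crossings near or after bedtime are plausible.

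**Working it through.** **Inputs.** Start 3.5 h (210 min) before bedtime, 30 min spacing, 20 min spacing in the last hour, end 2 h (120 min) after bedtime, 12 samples per visit (sections 10.2 and 10.4); 2 visits (section 10.4); 60 children (section 6.3).

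**The plan's totals.** 12 × 2 = 24 per child and 24 × 60 = 1,440. Both agree with section 6.3, so the totals follow from the 12 and are not separate errors.

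**Samples up to bedtime, counting both ends (minutes from bedtime).**
- Every 30 min: −210, −180, −150, −120, −90, −60, which is 6.
- Every 20 min: −40, −20, 0, which is 3.
- Sum: 9. Check on the gaps: 5 × 30 + 3 × 20 = 210 min.

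**After bedtime, with an assumed interval and a sample at +120.**

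| Assumed interval | Samples added | Per visit | Per child | 60 children | Difference from 1,440 |
|---|---|---|---|---|---|
| 20 min | 120/20 = 6 | 15 | 30 | 1,800 | +360 |
| 30 min | 120/30 = 4 | 13 | 26 | 1,560 | +120 |
| 40 min | 120/40 = 3 | 12 | 24 | 1,440 | 0 |

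**Other routes to 12.**
- 30 min spacing with the last sample at +90: 9 + 3 = 12. Here the 2 h mark closes the window and is not itself a sample time.
- 30 min spacing to +120 without the bedtime sample: 6 + 2 + 4 = 12.
- 30 min spacing to +120 without the −60 sample: 5 + 3 + 4 = 12.

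A uniform 30 min grid from −210 to +120 also gives 330/30 + 1 = 12, but it drops the 20 min spacing that the text states. It might explain where the 12 came from; that is conjecture.

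**Visit length.** Children enter 4.5 h before bedtime (section 10.2). Ending at +2 h gives 6.5 h and ending at +1.5 h gives 6.0 h, against roughly 7 h in section 10.3. This leans slightly towards the later end but does not settle the matter.

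**What differs between the readings.** Only the bracket for a crossing after bedtime (20, 30 or 40 min) and the last sample time (+90 or +120), apart from the single boundary point dropped in two of them. Section 1.0 puts preschoolers' bedtime on average 40 min after DLMO. A crossing at that average falls in the hour already sampled every 20 min. How often a crossing would fall after bedtime in this sample, and what a wider bracket would do to DLMO, cannot be computed from the protocol.

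**The case for a change.** The strongest case for a change is this. The protocol sets out to specify the timetable and does so twice, so it is not a matter left to an analysis plan. The most natural grammar extends the last-named interval of 20 min, which gives 15, the figure furthest from 12. Every route back to 12 adds something that the text does not say, and several incompatible schedules arrive there, so staff cannot derive the post-bedtime times from the document. The field in section 6.3 asks for the maximum number of specimens, and listing the times would cost a line of wording.

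Part of this stands. The post-bedtime interval and the last sample time are not stated, and a list would be tidier. The contradiction itself does not stand. The totals of 13 and 15 appear only after the reader supplies an interval for a window where the protocol gives none. Nine by bedtime is likewise a reading with both ends counted, because the text does not say whether each boundary point is sampled. Section 12.2 does not help: it describes returning to a reluctant child and is not a sampling schedule. The extra 120 or 360 specimens are hypothetical for the same reason.

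**Conclusion.** The schedule is incompletely written, but 12 per visit is not shown to be wrong. Three sections state or carry it consistently, and at least four timetables that fit the stated spacing before bedtime produce it. The gap is the spacing of about three or four samples in the two hours after bedtime, which the team must settle in order to run the visits at all.

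Writing the times down could leave 12, 24 and 1,440 exactly as they are. The timetable is anchored to each child's habitual bedtime and is common to all arms and both visits, so no between-arm bias is shown. Twelve samples spanning the stated window, with 20 min spacing in the last hour before bedtime, would give a sound DLMO under any of these timetables. No hypothesis, estimate or conclusion is shown to depend on which was meant.

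This rests on two assumptions: that the team collects the 12 samples it states, and that it uses the same timetable for every child. On that footing no change to the plan follows.

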Pre-assessment: During the initial phase of the study (pre-assessment), participants will come to the lab for 3 training visits to familiarize the child with the researchers, measure photosensitivity (pupillometry), cognitive performance (NIH Toolbox), and to introduce them to the saliva collection technique.

Baseline assessment: After the first pre-assessment visit, there will be a two-week at-home baseline assessment. Pre-intervention data will be collected on sleep timing (actigraphy), parent-reported sleep timing and behavioral sleep quality, light exposure (actigraph), and a baseline assessment of circadian timing (salivary DLMO). During 7 of the days (chosen by the subjects), parents will be asked to complete a daily diary of their child's screen media use. The second and third pre-assessment visits will occur during the baseline assessment period.

Randomization: Children will be randomly assigned to one of three two-week interventions (adjustment to home lighting, amber-tinted glasses, or clear glasses). Children will be randomized to the three conditions in a 2:2:1 ratio, stratified by sex. For each participant enrolled, a random number generator will provide a number from 1-30, which corresponds to an intervention condition for each sex.

Intervention Period: Changes in sleep timing and light exposure will be assessed throughout the intervention period via actigraphy, light sensing, and sleep diaries. Parents in the amber-tinted or clear glasses arms will also complete a daily diary detailing when the glasses are worn.

Post-intervention: After the intervention is complete, a secondary assessment of sleep timing via actigraphy (one week), light exposure, parent-reported questionnaires, cognitive performance, media diaries, and DLMO will be performed, as well as qualitative interviews with parents to assess child and family experiences. Interviews will not be audio- or video-recorded.

Throughout the duration of the study, the child will wear a wrist actigraph to record sleep timing and light history. Parents will complete a daily sleep diary, which documents children's sleep schedules and nocturnal awakenings.

5.A. Interventions

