De-identified data will be deposited into the National Sleep Research Resource repository.

Coded samples will be sent to Solid Phase Inc. for assaying. Solid Phase Inc will provide the assay results back to the UA study team.

15.0 Additional Questions (complete as applicable):

15.1 Subject Injury: If the research involves more than minimal risk to subjects, describe the provisions for medical care and available compensation in the event of research related injury. If the Human Research has a clinical trial agreement, this language should reflect what is stated in the agreement.

N/A

15.2 Withdrawal of Subjects: Discuss how, when, and why subjects may be removed from the study. If abrupt withdrawal is necessary, discuss how subjects will be withdrawn so that they are not put at increased risk. Discuss what happens if a subject is withdrawn from one part of the study but asked to continue with other parts, such as ongoing follow-up.

Because salivary melatonin is a main measure of the study, participants may be removed if it becomes evident during the training visits that they are not able to provide adequate saliva for samples. Subjects may also be removed from the study for consistently failing to complete study activities (e.g., not wearing the actiwatch or completing the sleep diaries). Any subject withdrawn from the study will receive pro-rated compensation commensurate with the sections of the study already completed.

15.3 Monitoring for Subject Safety: Provide a brief lay discussion of your plan to monitor for subject safety. Describe what safety information will be collected, including serious adverse events, how safety information will be collected, and the frequency of collection including a timeline of when the data and review(s) will occur, who will review the information, and the plan for reporting findings.

If there will not be a way to monitor for subject safety, please explain.

All adverse events will be recorded and reported to the IRB. Participants will have access to a phone number and email address through which to contact study personnel and in the case of any emergencies.

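### Section 15.2 lets the team remove randomised children for not completing study tasks and describes no further follow-up, so the second DLMO, the questionnaires and the parent interview can be lost

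*Protocol*

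**What the plan says.** Protocol section 15.2 gives two grounds for removal by the team. The first is inability to give enough saliva, and it is tied to the training visits. Section 10.2 places those visits before or during the two-week baseline. The second ground is: "Subjects may also be removed from the study for consistently failing to complete study activities". The examples given are not wearing the actiwatch and not completing the sleep diaries. No time limit is attached.

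The form's own prompt for 15.2 asks what happens when a subject leaves one part of the study but is asked to continue with others. The answer deals only with payment: "Any subject withdrawn from the study will receive pro-rated compensation commensurate with the sections of the study already completed".

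Both example activities continue after randomisation. Section 10.2 says: "Throughout the duration of the study, the child will wear a wrist actigraph to record sleep timing and light history". The sleep diary is daily over the same period. After the intervention, 10.2 plans one week of actigraphy, light exposure, and "parent-reported questionnaires, cognitive performance, media diaries, and DLMO will be performed, as well as qualitative interviews with parents". Within 10.2, part 5.B times the DLMO visits: "At the end of the baseline and intervention periods, the child will come to the laboratory for a circadian assessment". It places the parent interview after the post-intervention assessments.

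**The concern.** Removing a participant for poor task completion is harmless to the comparison if it happens before randomisation. Afterwards it removes a randomised child from outcome collection because of behaviour observed after assignment. As written, 15.2 permits this and says nothing about still collecting outcomes.

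Both main aims are exposed. Aim 1 (section 3.0) rests on compliance rates and the parent interviews, which ask about difficulties in carrying out the intervention. Families who could not keep up are plausibly among the most informative, and they can be removed before they are asked. The actiwatch is also the stated compliance measure for the home-lighting arm, so not wearing it is both a ground for removal and a gap in an Aim 1 measure. Aim 2 compares DLMO in each active arm with sham. A child who will not wear a watch may still give saliva, so losing that DLMO is avoidable. Only the two glasses arms keep an additional daily glasses diary, so the task burden, and hence removal, could differ by arm.

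Whether a DLMO or an interview is obtained at all is a matter of conduct fixed by the protocol. An analysis plan could model the missing values but could not recover them.

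**Working it through.** **The plan's own count.** Section 6.3 expects 60 children × 24 saliva samples = 1,440, which reproduces. The figure counts both DLMO evenings for every enrolled child. Section 15.4 likewise describes a final dataset of 60. No replacement of removed children is described.

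**Timeline.**

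| Period | Weeks | Removal for non-completion allowed? | Outcomes still to come |
|---|---|---|---|
| Baseline (before randomisation) | 2 | yes | child not yet randomised |
| Intervention | 2 | yes | second DLMO, questionnaires, cognitive battery, media diaries, interview |
| Post-intervention | 1 | yes | at least the interview |

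The rule therefore applies during 2 + 1 = 3 of the 5 study weeks after randomisation. If removal ends participation, a child removed during the intervention provides none of the outcomes in that row. A family removed in the last week loses at least the interview. Little actigraphy is lost if the watch was not being worn.

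**Arm sizes.** The ratio is given by "Children will be randomized to the three conditions in a 2:2:1 ratio, stratified by sex", and the 30 per sex by "a random number generator will provide a number from 1-30, which corresponds to an intervention condition for each sex".

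- Overall: 60 × 2/5, 60 × 2/5, 60 × 1/5 = 24, 24, 12.
- Within each sex: 30 × 2/5, 30 × 2/5, 30 × 1/5 = 12, 12, 6.

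**Interviews lost per removal.** Active arm 1/24 = 4.2%; sham arm 1/12 = 8.3%; sham within one sex 1/6 = 16.7%.

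**Precision of one active-versus-sham contrast.** Assuming equal variances, the standard error in SD units is √(1/n_active + 1/n_sham). At full size this is √(1/24 + 1/12) = 0.3536.

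| Active | Sham | SE (SD units) | Increase |
|---|---|---|---|
| 23 | 12 | 0.3561 | 0.7% |
| 22 | 12 | 0.3589 | 1.5% |
| 21 | 12 | 0.3619 | 2.4% |
| 24 | 11 | 0.3641 | 3.0% |
| 24 | 10 | 0.3764 | 6.5% |
| 24 | 9 | 0.3909 | 10.6% |
| 22 | 11 | 0.3693 | 4.4% |
| 20 | 10 | 0.3873 | 9.5% |

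The last two rows apply if removal is unrelated to arm. The rows with losses in only one arm show the range. The protocol gives no removal rate, so these are effects per given number removed, not forecasts.

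**The case against.** The strongest reply is that nothing in 15.2 is false or contradictory. Removal is optional, it requires persistent failure, and the protocol nowhere says later data would be refused. The actigraph and diary also run through a two-week baseline before randomisation, so many non-completers should show themselves in time. This stands, and it means the loss is possible rather than certain. It does not remove the point: the rule remains available after randomisation, and the only consequence it states is payment for completed sections.

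Second, the named triggers are measurement tasks, not use of the glasses or bulbs. That removed families are the ones who struggled with the intervention is therefore inference. This is fair, and the point is put here as plausible, not shown.

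Third, section 12.2 already lets the team skip a saliva sample, or stop an activity, without ending participation. That provision concerns a child's discomfort during an activity. It does not govern removal for non-completion.

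Fourth, the precision figures assume that the fix would recover every removed child. A family that neglects daily tasks may also decline a DLMO visit that section 10.3 puts at about 7 hours. The sham-only rows are also an extreme, since there is no evidence that removals would fall in that arm. Both are right: the figures are upper bounds on what the fix would save.

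**Conclusion.** The concern holds. Section 15.2 permits removal for non-completion after randomisation and describes no continued follow-up. Used as written, it creates avoidable and possibly selective loss of Aim 1 and Aim 2 outcomes. The effect on precision is modest: 0.7% on the standard error for one active child lost, 3.0% for one sham child, and 4.4% for two active and one sham. The 12-child sham arm is the most exposed, at 8.3% of its interviews per removal. Selective loss is the larger risk and cannot be quantified from the protocol.

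This rests on removal ending outcome collection, on no replacement, and on equal variances for the precision figures. The frequency of removal is unknown. It should be fixed because the change is cheap; confidence in its practical importance is medium.

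**What to change.** In 15.2, limit removal for non-completion of actigraphy, diaries or other study activities to the period before randomisation. State that after randomisation the post-intervention DLMO, questionnaires and any available actigraphy will still be sought where the family agrees. In 10.2, offer the existing 30-minute interview to families who stop early.

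The DLMO visit is timed from "average parent-reported bedtime across previous five days". Where the diary has not been kept, ask the parent for those bedtimes when scheduling, so that the visit can still take place.

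This concerns data collection only. It does not bear on whether a child goes on using the glasses or bulbs, and the family's right to withdraw at any time is unchanged.

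The cost is wording in two sections. No new procedure is added, and the payments are already in the section 13.2 compensation schedule: $20 surveys + $80 in-lab assessment + $20 interview = $120, or $160 with the $40 for actigraphy, of the $400 per family. The downside is that some retained children will have incomplete actigraphy or diaries, and feasibility may look less favourable.
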